2.5.3 Handling of missing values/censoring/discontinuations

Patients who do not have a valid PASI assessment at week 28 will be regarded as non-responders for the primary analysis.

2.5.4 Sensitivity analyses

The primary endpoint will be analyzed by means of a Cochran-Mantel-Haenszel (CMH) test using the FAS set. This test will be stratified by center. Treatment groups will be compared with respect to the proportion of responders using the CMH test statistics. The corresponding p-values will be based on the CMH statistics which follows a Chi-square distribution with one degree of freedom.

2.6 Analysis of secondary efficacy objective(s)

2.6.1 Analysis of secondary endpoints

PASI 75, 90 and 100 at weeks 1, 2, 3, 4, 8, 12, 16, 20, 24 and 28 will be analyzed analogous to the primary endpoint. Absolute PASI scores will be analyzed using a MMRM, with factors treatment, center, visit, visit*treatment interaction and covariate baseline PASI. The raw as well as the adjusted least squares means and their differences between treatment groups will be calculated for each visit together with their corresponding 95% confidence intervals and p-values.

The same MMRM model updated with relevant baseline covariate similar to primary endpoint will also be used for the analyses of the other continuous secondary endpoints hsCRP, HbA1c, fructosamine, fasting plasma glucose, LDL, HDL, total cholesterol, triglycerides, waist circumference, BMI, body weight, systolic and diastolic blood pressure, QoL-scores (Absolute DLQI total score, relative change from baseline of DLQI total score, absolute WHO-5 total score, relative change from baseline in WHO-5 total score, absolute self-assessed itch, pain, and scaling, relative change from baseline in self-assessed itch, pain, and scaling) and activity levels (steps per day).

All the patients reporting DLQI score = 0 or 1 will be considered as “Responders (0)”, whereas the patients reporting DLQI score ≥ 2 will be considered as “Non-responders (1)”.

Proportion of patients with DLQI score (0&1) i.e., DLQI responders will be evaluated in both the arms and will be compared using a logistic regression model with the factors treatment, center, visit, visit*treatment interaction and covariate baseline DLQI. The odds ratio and its 95% confidence interval (CI) and p-value will be reported. See [Appendix 5.3](#) for more details on PROs.

Note: For the subjects with fasting & non-fasting status, separate analyses will be performed for fasting plasma glucose, fructosamine, and HbA1c levels.

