9.5 Analysis of secondary variables

9.5.1 Efficacy variables

PASI 75, 90 and 100 at weeks 1, 2, 3, 4, 8, 12, 16, 20, 24 and 28 will be analyzed analogous to the primary endpoint. Absolute PASI scores will be analyzed using a Mixed Model for Repeated Measurements (MMRM) with factors treatment, center, visit, visit*treatment interaction and covariate baseline PASI. The raw- as well as the adjusted (LS-) means and their differences between treatment groups will be calculated for each visit together with their corresponding 95% confidence intervals and p-values.

The same MMRM model will also be used for the analyses of the other continuous secondary endpoints hsCRP, HbA1c, fructosamine, fasting plasma glucose, LDL, HDL, cholesterol, triglycerides, waist circumference, body weight, BMI, systolic and diastolic blood pressure, absolute DLQI, relative change of DLQI, proportion of patients with DLQI 0/1, absolute WHO-5, relative change in WHO-5, absolute self-assessed itch, pain, scaling, relative change in self-assessed itch, pain, scaling in both treatment arms throughout the duration of the core study, and activity levels.

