2.11 Interim analysis

A first analysis of the core study (primary, secondary [REDACTED] endpoints related to the core study) will be performed after all subjects have completed the core study.

[REDACTED]

The two analyses will be reported in separate clinical study reports.

3 Sample size calculation

This study is primarily designed to demonstrate superiority of secukinumab combined with lifestyle intervention vs Secukinumab alone in terms of PASI90 response at week 28. A PASI90 response of 81% at week 28 under Secukinumab alone in patients with metabolic syndrome is assumed. This number is based on a retrospective analysis performed with data from the CLEAR study, taking into account the slightly higher BMI of the patient population with metabolic syndrome (BMI 23-42 kg/m², Albareda M et al., 2014) and the open-label design.

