Evidence on effect size of lifestyle intervention on PASI response is relatively rare and assumptions were based on the following studies: A clinical study by [Al-Mutairi et al \(2014\)](#) showed an absolute increase of 27% in PASI75 response to biologic treatment (Infliximab, Etanercept, Ustekinumab, Adalimumab) in overweight or obese, moderate to severe psoriasis patients undergoing weight reduction compared to patients not undergoing weight reduction. However the dietary regimen used in this study was highly restrictive and consecutively led to a strong mean weight loss (-13 kg vs + 1,5 kg in the control group after 24 weeks). Naldi et al (2014) showed an absolute increase of 6% in PASI75 response to systemic treatment in overweight to obese, moderate to severe psoriasis patients undergoing diet and physical exercise compared to control patients. The lifestyle intervention in this study was less intensive and consecutively led to a smaller mean weight loss (-3kg vs -1.6 kg in the control group after 20 weeks). It seems that the extent of increase in PASI response correlates with the achieved weight loss, at least to a certain extent. PASI90 data were not available for both cited studies. The lifestyle intervention conducted in the present study is less intensive than the one applied by Al-Mutairi et al. but more intensive compared to Naldi et al. A lifestyle intervention very similar to the one applied in our study was previously able to show a mean weight loss of -3.8 kg vs. - 1.4 kg after 1 year (Kulzer B et al., 2014). Maximum weight loss can already be expected after 3-4 month. As part of the lifestyle intervention program activity tracking devices will be used in the present study to further support the lifestyle intervention.

Based on these considerations and the fact that we are looking at PASI90 response in the present study, we assume an absolute increase of 9% in PASI90 response in the Secukinumab combined with lifestyle intervention arm to 90% PASI90 responders compared to 81% PASI90 responders in the Secukinumab alone arm. An absolute increase of 9% in PASI90 responders would also be clinically meaningful.

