5.1 Statistical models

MMRM Model

Absolute biomarkers value will be analyzed using a Mixed Model for Repeated Measurements (MMRM) with factors treatment, center, visit, visit*treatment interaction and covariate baseline biomarker value.

```
proc mixed data = BAS covtest;  
class subjid TRT01P siteid avisitn;  
model CHG_B = base TRT01P siteid avisitn avisitn*TRT01P/ ddfm=KR  
residual;  
repeated avisitn / type=un subject=subjid rcorr;  
estimate "Trt diff at Week 28" Trt 1 -1 TRT01P*avisitn 1 -1/cl;  
lsmeans Trt*VisitWk / cl;  
run;
```

Where,

BAS = dataset; TRT01P = Treatment arms (A & B); CHG_B = Change from Baseline

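### The MMRM for absolute PASI has no baseline-by-visit term, so the per-visit treatment differences lose some precision, mostly at Weeks 1 and 2

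*SAP*

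**What the plan says.** SAP 2.6.1 gives the model for absolute PASI: "Absolute PASI scores will be analyzed using a MMRM, with factors treatment, center, visit, visit*treatment interaction and covariate baseline PASI". Protocol 9.5.1 lists the same terms: "with factors treatment, center, visit, visit*treatment interaction and covariate baseline PASI". Neither has a baseline-by-visit interaction.

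Adjusted means and their differences are to be "calculated for each visit together with their corresponding 95% confidence intervals and p-values". Absolute PASI is a listed secondary endpoint at Weeks 1, 2, 3, 4, 8, 12, 16, 20, 24 and 28 (SAP Table 1-1, Protocol Table 2-1).

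SAP 2.6.1 carries the model, with the relevant baseline, to the other continuous secondary endpoints. The biomarker SAP does the same, and its code in section 5.1 confirms the literal reading, with baseline as a main effect only: "model CHG_B = base TRT01P siteid avisitn avisitn*TRT01P/ ddfm=KR". That code also requests an unstructured covariance ("repeated avisitn / type=un subject=subjid rcorr"). The main SAP states no covariance structure for its MMRM.

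**The concern.** A single baseline slope suits an outcome whose dependence on baseline is stable over time. PASI in this trial is unlikely to behave that way.

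- **Week 28.** SAP section 3 (Sample size calculation) states "A PASI90 response of 81% at week 28 under Secukinumab alone in patients with metabolic syndrome is assumed", rising "to 90% PASI90 responders compared to 81% PASI90 responders in the Secukinumab alone arm". A PASI90 responder has at most a tenth of the baseline score left, so in most patients the score then carries little of the baseline.
- **Week 1.** Efficacy is assessed before that visit's injection (Protocol 6.4), and injections are at Weeks 0, 1, 2 and so on (Protocol 5.2). The Week 1 score therefore follows a single dose and must depend on baseline much more than the Week 28 score does.

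The fitted slope is a compromise between these extremes. Where it is far from the true slope, baseline variation that could have been removed stays in the residual, and the confidence interval for that visit is wider than it needs to be. At stake is the precision of the per-visit secondary comparisons.

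**Working it through.** **1. The plan's own figure.** The documents give no figure for MMRM precision. The one relevant calculation, for the primary endpoint, reproduces. For 81% versus 90%, two-sided 0.05 and 90% power, the two-proportion formula gives 320 per arm without and 342 with continuity correction; the plan states 342. At 342 per arm the continuity-corrected power is 90.1% for 9 points and 74.7% for 7.5 points (stated: 90% and 75%). Allowing 10% dropout, 342/0.90 = 380. None of this depends on the MMRM.

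**2. Formula.** Assume complete data and unstructured covariance, and leave center aside. Let β_j be the true baseline slope at visit j, s_j the residual SD given baseline, S the residual covariance matrix and σ_B the baseline SD. The common slope settles at

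b = (1'S⁻¹β) / (1'S⁻¹1).

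The treatment estimate at visit j is the difference in mean outcome minus b times the difference in mean baseline. Its variance is proportional to s_j² + (β_j − b)²σ_B². With visit-specific slopes it is proportional to s_j². Hence

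information lost at visit j = (β_j − b)²σ_B² / [s_j² + (β_j − b)²σ_B²].

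**3. One scenario in full.** All inputs are assumed: σ_B = 8, slope falling from 0.85 to 0.05, residual SDs as in the table, autoregressive correlation 0.7. This gives b = 0.2045. The last column is a simulation of 1,500 trials with 342 per arm.

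| Week | β | s | (β − b)·8 | squared | loss | simulated |
|---|---|---|---|---|---|---|
| 1 | 0.85 | 5 | 5.16 | 26.7 | 26.7/51.7 = 52% | 54% |
| 2 | 0.65 | 6 | 3.56 | 12.7 | 12.7/48.7 = 26% | 28% |
| 3 | 0.50 | 6 | 2.36 | 5.6 | 5.6/41.6 = 13% | 15% |
| 4 | 0.35 | 6 | 1.16 | 1.35 | 1.35/37.35 = 4% | 5% |
| 8 | 0.18 | 5 | −0.20 | 0.04 | 0.04/25.04 = 0% | 0% |
| 28 | 0.05 | 3 | −1.24 | 1.53 | 1.53/10.53 = 15% | 18% |

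At Week 1 the standard error with visit-specific slopes would be √(1 − 0.52) = 0.69 of that under the common slope.

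**4. Range.** A grid of 90 assumed scenarios used Week 1 slope 0.75-0.95, Week 28 slope 0.03-0.10, baseline SD 6, 8 or 10, residual SD 2-6 and two correlation patterns. The losses (minimum / median / maximum) were:

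- Week 1: 14 / 55 / 88%
- Week 2: 6 / 35 / 78%
- Week 3: 2 / 19 / 71%
- Week 4: 0 / 4 / 62%
- Week 28: about 4% to 60%

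Because nothing in the documents fixes the Week 1 slope, it was then varied from 0.4 to 0.9. Median losses were about 17-56% at Week 1, 10-42% at Week 2, 3-17% at Week 4 and 3-16% at Week 28. The path of the slope between Weeks 1 and 28 is also assumed and shifts these figures. In an exponential-clearance simulation, where late PASI varies little, the loss at Week 28 was only 0-1%.

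**5. Bias and standard errors.** In the step 3 simulation, under no treatment effect, the mean error was at most 0.04 PASI points at any visit. Model standard error divided by empirical SD was 0.96-1.01. The unstructured covariance absorbs the misfit, so the intervals are wider than necessary but about right for the estimator used.

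**The case against.** The case for leaving the model alone is substantial.

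- **It is prespecified and valid.** Protocol and SAP agree, the PASI objective is worded as exploratory, and the primary analysis is a logistic regression at Week 28. All of this stands; the point concerns efficiency only.
- **The visits that lose most matter least.** Both arms receive the same secukinumab, and Protocol 3.3 expects optimal weight loss only after about 3 to 4 months, so little difference between arms is expected at Weeks 1 and 2. This stands and limits the practical value of the gain. The loss at Week 28 is smaller in most scenarios, though not always nil.
- **The inputs are missing.** No baseline SD, slope or residual SD is given, and the non-responders, who carry most of the remaining PASI, prevent the 81-90% figure from fixing the Week 28 slope. This stands for the size of the loss. It does not make a constant slope plausible.

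Three stronger readings are tempting, and the documents do not support them. A reader might infer that the slope is near 1 at Week 1 and near 0 at Week 28, so that early visits lose a quarter to a half of their information. Those slopes are not in the documents, and in the 90 scenarios only 12% to 49% fell in that band at each of Weeks 1 to 4. A reader might infer bias, particularly with missing data; no missing-data mechanism was examined, and with complete data the estimates were essentially unbiased. A reader might also infer a similar cost for every endpoint sharing the model. A stable HbA1c-like marker lost only about 6% in simulation, and the biomarker sub-study has just two post-baseline visits and no formal hypothesis testing.

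**Conclusion.** The point holds as a modest efficiency gain for secondary endpoints. One baseline slope for all ten PASI visits is implausible given the plan's own Week 28 assumption, and it costs precision in the per-visit differences. The loss falls mainly at Weeks 1 and 2, is usually small by Week 4, and may reappear to a lesser degree at Week 28.

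The size rests wholly on the assumed slopes, SDs and unstructured covariance, with complete data. The direction rests only on PASI depending less on baseline at Week 28 than at Week 1. The conclusions of the primary analysis do not turn on this.

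**What to change.** In SAP 2.6.1, specify the MMRM for absolute PASI with treatment, center, visit, treatment*visit, baseline PASI and baseline PASI*visit, and state an unstructured covariance, as the biomarker code already does. Record the added term in SAP section 4, because Protocol 9.5.1 lists the model without it. Use the same term, with each endpoint's own baseline, for the other continuous secondary endpoints and in biomarker SAP 2.5.2 and 5.1, where the gain will usually be small.

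**Cost.** Ten slopes replace one, so at most 9 degrees of freedom with about 760 patients; in the biomarker sub-study two slopes replace one, so 1 degree of freedom with 100 patients. No new data are needed, and if the slopes turn out to be constant almost nothing is lost.

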2.5.2 Statistical hypothesis, model, and method of analysis

The null hypothesis to be rejected is that the odds of response Week 28 are equal in both treatment groups. The corresponding alternative hypothesis is that the odds of response at Week 28 are higher under Secukinumab combined with lifestyle intervention compared to Secukinumab alone.

Let p_j denote the proportion of responders at Week 28 for treatment group j , $j=0, 1$, where

- 0 corresponds to Secukinumab combined with lifestyle intervention
- 1 corresponds to Secukinumab alone

The following hypotheses will be tested:

$$H_0: (p_1 / (1 - p_1)) / (p_0 / (1 - p_0)) = 1 \text{ versus } H_A: (p_1 / (1 - p_1)) / (p_0 / (1 - p_0)) \neq 1$$

In other words:

H_A : The odds ratio of achieving a response at Week 28 for Secukinumab combined with lifestyle intervention vs Secukinumab alone is different from 1.

The primary analysis will be performed on FAS dataset comparing treatments with respect to the primary efficacy variable in a logistic regression model with the factors treatment, center and covariate baseline PASI. The odds ratio and its 95% confidence interval (CI) and p-value will be given. The null hypothesis of equal odds will be rejected if the 2-sided p-value from the

logistic regression model for the factor “treatment” is < 0.05 ; however, superiority of Secukinumab combined with lifestyle intervention will be claimed only if the direction is correct, i.e. if the odds of response are larger under Secukinumab combined with lifestyle intervention.

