5.2 Statistical models

5.2.1 Primary analysis

Logistic regression model

The proportions of patients who achieve a PASI 90 response at Week 28 for each treatment group will be compared using logistic regression analysis. The model will include treatment and center as fixed effect and with covariates PASI score at baseline (Visit 2).

The SAS procedure PROC GLIMMIX will be used with the following SAS code:

```
proc glimmix data=.... order=internal;  
class trtn1 cntr ;  
model response = trtn1 cntr basv2 / ddfm=kr error=binary  
link=logit;  
lsmeans trtn1 / cl diff oddsratio;  
run;
```

where

response = PASI 90 response (= 1 or 0)

trtn1 = treatment

cntr = center

basv2 = PASI score at baseline (Visit 2)

The estimated odds ratios will be displayed along with the associated 95% confidence intervals and p-values (two-sided).

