5.3 Patient reported outcomes (PRO)

PROs will be assessed by the following validated instruments.

- Dermatology Life Quality Index (DLQI®)
- Self-assessed pain, itching, scaling
- WHO-5

Dermatology Life Quality Index (DLQI®)

The DLQI® is a 10-item general dermatology disability index designed to assess Health-related quality of life (HRQoL) in adult subjects with skin diseases such as eczema, psoriasis, acne, and viral warts (Finlay and Khan, 1994; Basra et al., 2008).

The measure is self-administered and includes domains of daily activities, leisure, personal relationships, symptoms and feelings, treatment, and work/school. The measure is widely used: it has been tested across 33 different skin conditions and is available in 85 languages. The DLQI is the most frequently used instrument in studies of randomized controlled trials in dermatology. The recall period is the previous week, and the instrument takes 1 to 2 minutes to complete.

Each item has four response categories including 0 (not at all), 1 (a little), 2 (a lot), and 3 (very much). "Not relevant" is also a valid response and is scored as 0.

The DLQI[®] total score is the sum of the 10 questions. Scores range from 0 to 30, with higher scores indicating greater HRQoL impairment. Each subscale of the DLQI[®] may also be analyzed separately.

Meaning of DLQI Scores

- 0-1= no effect at all on subject's life
- 2-5= small effect on subject's life
- 6-10= moderate effect on subject's life
- 11-20= very large effect on subject's life
- 21-30= extremely large effect on subject's life

DLQI response 0/1 variable will be calculated based on the DLQI total score as follows:

- 0 – If DLQI total score is either 0 or 1
- 1 – If DLQI total score is > 1

DLQI percentage change from baseline will be calculated using DLQI total scores as follows:

$$((\text{post-baseline total DLQI} - \text{baseline total DLQI}) / (\text{baseline total DLQI})) * 100$$

Subject's self-assessed pain, itching and scaling

A self-administered, 11-point numeric rating scale (NRS, 0-10) will be used to evaluate the subject's assessment of their current pain, itching and scaling. Respondents will answer the following questions for the assessment of

- **Pain:** Overall, how severe was your psoriasis-related pain over the past 24 hours
- **Itching:** Overall, how severe was your psoriasis-related itch over the past 24 hours
- **Scaling:** Overall, how severe was your psoriasis-related scaling over the past 24 hours

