5.3 Patient reported outcomes (PRO)

PROs will be assessed by the following validated instruments.

- Dermatology Life Quality Index (DLQI®)
- Self-assessed pain, itching, scaling

- WHO-5

Dermatology Life Quality Index (DLQI®)

The DLQI® is a 10-item general dermatology disability index designed to assess Health-related quality of life (HRQoL) in adult subjects with skin diseases such as eczema, psoriasis, acne, and viral warts (Finlay and Khan 1994; Basra et al 2008).

The measure is self-administered and includes domains of daily activities, leisure, personal relationships, symptoms and feelings, treatment, and work/school. The measure is widely used: it has been tested across 33 different skin conditions and is available in 85 languages. The DLQI is the most frequently used instrument in studies of randomized controlled trials in dermatology. The recall period is the previous week, and the instrument takes 1 to 2 minutes to complete.

Each item has four response categories including 0 (not at all), 1 (a little), 2 (a lot), and 3 (very much). “Not relevant” is also a valid response and is scored as 0.

The DLQI® total score is the sum of the 10 questions. Scores range from 0 to 30, with higher scores indicating greater HRQoL impairment. Each subscale of the DLQI® may also be analyzed separately.

Meaning of DLQI Scores

- 0-1= no effect at all on subject's life
- 2-5= small effect on subject's life
- 6-10= moderate effect on subject's life
- 11-20= very large effect on subject's life
- 21-30= extremely large effect on subject's life

DLQI response 0/1 variable will be calculated based on the DLQI total score as follows:

- 0 (Responders) – If DLQI total score is either 0 or 1
- 1 (Non-Responders) – If DLQI total score is > 1

Subject's self-assessed pain, itching and scaling

A self-administered, 11-point numeric rating scale (NRS, 0-10) will be used to evaluate the subject's assessment of their current pain, itching and scaling. Respondents will answer the following questions for the assessment of

- **Pain:** Overall, how severe was your psoriasis-related pain over the past 24 hours
- **Itching:** Overall, how severe was your psoriasis-related itch over the past 24 hours
- **Scaling:** Overall, how severe was your psoriasis-related scaling over the past 24 hours

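### DLQI 0/1 is coded 0 = responder while PASI90 is by implication 1 = responder, and no event level or treatment contrast is named, so an odds ratio could be reported as its reciprocal

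*SAP*

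**What the plan says.** **DLQI 0/1.** SAP 2.6.1 states "All the patients reporting DLQI score = 0 or 1 will be considered as" responders, labelled 0, and labels scores of 2 or more as non-responders, 1. SAP 5.3 repeats this: "DLQI response 0/1 variable will be calculated based on the DLQI total score as follows", followed by "0 – If DLQI total score is either 0 or 1" and a 1 for totals above 1. The extension SAP, section 5.3, uses the same direction and adds the responder and non-responder labels. SAP 2.6.1 asks for a logistic regression on this endpoint with odds ratio, 95% CI and p-value, but gives no code for it.

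**PASI90.** SAP 5.2.1 gives the only logistic code in the plan. Its model line is "model response = trtn1 cntr basv2 / ddfm=kr error=binary", and its key reads "response = PASI 90 response (= 1 or 0"). No event level is named. `trtn1` is explained only as treatment, without level values or a reference arm.

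**Hypothesis.** In SAP 2.5.2 index 0 is the combination and "1 corresponds to Secukinumab alone". The symbols then divide the odds of group 1 by the odds of group 0. The sentence that explains them reads: "The odds ratio of achieving a response at Week 28 for Secukinumab combined with lifestyle intervention vs Secukinumab alone is different from 1". Protocol 9.4.2 has the same symbols and the same explanation.

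**Decision rule.** Both documents claim superiority only when the two-sided p-value is below 0.05 and the odds of response are larger with the combination.

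**The concern.** A logistic odds ratio has a direction only once two things are fixed: which outcome level is the event, and which arm is in the numerator. The plan fixes neither in its code, and its two binary endpoints appear to run in opposite directions. A programmer who reuses one convention for both will produce one odds ratio for response and one for non-response.

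The p-value cannot reveal this, because it is the same either way. What changes is the printed odds ratio and its confidence interval, and a reader takes benefit or harm from those. The hypothesis does not settle the direction, because its symbols and its words are reciprocals of each other.

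**Working it through.** **Inputs.** Planned PASI90 rates are 90% (combination) and 81% (alone), with 342 per arm, 90% power and two-sided alpha 0.05 (protocol 9.8, SAP 3). Allocation is 1:1 (protocol 5.3).

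**Plan's own figure.** The two-proportion formula with continuity correction at 81% and 90% gives 342 per arm, an exact match (320 without the correction). The rates used below are therefore those behind the sample size.

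**Odds ratio at the planned rates.**
- Odds of response, combination: 0.90/0.10 = 9.00
- Odds of response, alone: 0.81/0.19 = 4.263
- Combination versus alone: 9.00/4.263 = 2.11
- Reciprocal: 1/2.11 = 0.474

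**All four direction choices.** Whole-number counts close to those rates are 308/342 (combination) and 277/342 (alone). By hand, (308/34)/(277/65) = 9.059/4.262 = 2.13. Logistic fits with treatment only give:

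| Event modelled | Contrast | Odds ratio (95% CI) | p |
|---|---|---|---|
| response | combination vs alone | 2.13 (1.36 to 3.32) | 0.0009 |
| non-response | combination vs alone | 0.470 (0.301 to 0.734) | 0.0009 |
| response | alone vs combination | 0.470 (0.301 to 0.734) | 0.0009 |
| non-response | alone vs combination | 2.13 (1.36 to 3.32) | 0.0009 |

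One flip gives the reciprocal; two flips cancel.

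**Applying one convention to both endpoints** (taking PASI90 1 = responder, as implied):

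| Level taken as event | PASI90 odds ratio is for | DLQI 0/1 odds ratio is for |
|---|---|---|
| 1 | response | non-response |
| 0 | non-response | response |

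Whichever level is taken, the two odds ratios are on opposite scales. This follows from the stated codings and needs no assumption about software.

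**Hypothesis.** The symbols are odds(alone)/odds(combination), 0.47 at the planned rates. The words are odds(combination)/odds(alone), 2.11. The null is ratio = 1 and the alternative is ratio ≠ 1. Both are unchanged by taking the reciprocal, so the test is the same.

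**The case against.** The strongest reply is that nothing decisive depends on this. The superiority rule is written in words, on the odds of response, and is not tied to a printed odds ratio above 1. The primary variable is the percentage of responders in each arm, so a reciprocal odds ratio would visibly contradict the percentages. The inverted symbols do not touch a two-sided test, and the code does not use those indices. All of this stands.

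It can also be said that shared code is an assumption. SAP 5.2.1 belongs to the primary analysis, while the DLQI model adds visit and visit-by-treatment terms and has no code. SAP 2.6.1 also says in words that DLQI responders are compared, and the DLQI coding is consistent wherever it appears. This is fair, and it is why the point is conditional. But the plan asks for a DLQI odds ratio and leaves its event level open, on a coding opposite to the one implied for the primary endpoint.

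A reader might infer that some odds ratio is bound to point the wrong way. The documents do not support that: the event level and the `trtn1` contrast are both open, and two flips cancel. A reader who knows the software might infer that its default event level makes PASI90 the affected endpoint. The documents state no default, so that inference is not used here.

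**Conclusion.** The specification is defective in a limited way. The codings run in opposite directions (for PASI90 by implication), the event level and treatment contrast are not named, and the symbolic hypothesis is the reciprocal of its explanation. An odds ratio and its interval could therefore be reported as the reciprocal: 0.47 instead of 2.11 at the planned rates. The most plausible case is DLQI 0/1. The plan gives no DLQI response rates, so the PASI90 figures only illustrate the size; the reciprocal relation holds at any rates.

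P-values, power, the 342 per arm and the superiority rule are unaffected.

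Three wider readings are tempting and not supported:
- **The secondary PASI endpoints clash too.** The 3 × 10 = 30 PASI 75/90/100 comparisons are analysed like the primary endpoint, and one of them is the primary endpoint (PASI90 at week 28). They would share its direction, so the DLQI conflict does not reach them. They share only the unnamed event and contrast.
- **Extension results are reversed.** The visible patient-reported analysis in the extension SAP is descriptive (2.7) and it lists no statistical model (5.2), so no visible odds ratio there depends on the coding.
- **Missing DLQI values would become responders.** SAP 2.6.2 states the imputation in words as non-responder, which under the present coding means 1. Nothing says missing values are set to 0.

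**What to change.** 1. Code responder = 1 and non-responder = 0 for every binary endpoint. For DLQI 0/1 this changes SAP 2.6.1, SAP 5.3 and extension SAP 5.3. Missing values under non-responder imputation then take 0 on every endpoint.
2. State in SAP 5.2.1 that PASI90 response = 1 means responder, and name the event in every logistic model, for example `response(event='1')`. Add code for the DLQI model.
3. Define the levels of `trtn1` and state that the reported odds ratio is combination versus secukinumab alone. Naming the event without this leaves half of the direction open.
4. In protocol 9.4.2 and SAP 2.5.2, write the ratio as (p0/(1−p0))/(p1/(1−p1)), to agree with the sentence that explains it.
5. Check each reported odds ratio against the raw responder percentages by arm.

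The cost is SAP and protocol wording, one recoded variable and one option per model. There is no statistical downside, and no test, sample size or decision rule changes.
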